The following validated questionnaires are also administered at 6 and 12 month follow up:

- EQ-5D
- Smoking Cessation and Health Service Use Questionnaire

Timing of data collection

The recruitment period was: 11 May 2015 – 01 February 2017 (22 months) and the study sessions were conducted as follows:

Week -1	Baseline
Week 0:	Randomisation (TQD)
Weeks 1-4:	Treatment sessions, 1, 2, 3 and 4 weeks post TQD (Q+1, Q+2, Q+3 and Q+4)
Month 6:	Follow-up, 24 weeks post TQD (Q+24)
Month 12:	Follow-up, 52 weeks post TQD (Q+52)

Database

Description

Data were entered into the online database, 'Oracle Database 11g', hosted at the Barts Cancer Centre. The Electronic Data Capture forms are web based and built using Java with data validation in JavaScript (Java framework Struts 2).

Data quality

The study team check the data for discrepancies each week, and clarify any potential data entry errors with the relevant advisor/researcher or participant. When recruitment and follow-up are complete, the study team will clean the data in the following way: values for each variable will be sorted, and those at the extremes will be checked to ensure that they are within the expected range.

Source data verification will also be conducted where paper CRFs have been used: a random sample of 10% of CRFs will be selected, and the study team will compare all written entries with those entered onto the main study database. The pre-specified data quality target is $\leq 2\%$ discrepancy rate between entries in the CRF and the electronic database. If an error is found in $>2\%$ of entries, the quality target for data entry will not have been met, and all CRF data will be cross-checked against data in the study database.

Derived and computed variables

All derived and computed variables will be documented in the analysis programmes.

General issues for statistical analysis

General analysis principles

The main analysis for each outcome will use intention-to-treat (ITT) principles, meaning that all participants with a recorded outcome will be included in the analysis, and will be analysed according to the treatment group to which they were randomised. More information on which participants will be included in each analysis is available in the section below. All p-values will be two sided, and the significance level is set at 5%.

Analyses for all outcomes will be presented as:

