***See appendix 3 for how data for each outcome was collected**

Differences in tobacco withdrawal symptoms at 1 and 4 weeks.

Between-group differences in urges to smoke, and changes (from baseline) in tobacco withdrawal symptoms will be examined using ANOVA, in both the whole sample, and abstainers only sample.

Treatment ratings (e.g. satisfaction, taste, helpfulness, reasons for stopping product use)

Differences in mean ratings of treatment effects (product helpfulness, taste, satisfaction and reasons for stopping product use) between groups will be examined using ANOVA (or non-parametric tests where normality cannot be assumed) at 1 and 4 weeks post quit with adjustments where needed for normal distribution. NB. Where 2 NRT products were used and rated, the average rating of the two will be taken.

Adverse reactions (ARs)

The frequency of participants reporting each AR (nausea, sleep disturbance or throat/mouth irritation) at least once will be compared between arms using Chi squared test. The MedDRA coding system will be used.

Changes in respiratory problems

Frequency of respiratory problems at baseline and 12 month follow up will be compared between arms using Chi-squared test.

Cost-efficacy of the interventions.

The economic evaluation is conducted alongside the TEC trial by way of a cost-effectiveness analysis. Following NICE guidance, the analysis will be performed from the National Health Service (NHS) and Personal Social Services (PSS) perspective to reflect NHS England decision-making framework [16]. The analysis from a wider perspective will also be conducted to explore the possible societal impact of the intervention. All costs will be presented in 2015/16 Sterling Pounds (£). The objectives of the analysis are:

1. To assess cost-effectiveness of EC over and above UC at 12-month follow-up (primary outcome);
2. To estimate potential long term cost-effectiveness of the intervention.

These objectives will be achieved by combining data collected within the trial and existing models.

Costs estimation

Intervention cost

The intervention consists of six weekly sessions of standard SSS behavioural support for both arms, a starter kit of e-cigarette for the EC arm and supplies of NRT for the UC arm.

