7-day point prevalence at 52 weeks post TQD, N (%)						

Table 6 – Change in respiratory symptoms

	NRT (N=)		EC (N=)		P-value	Odds Ratio (95% CI)
	Baseline N (%)	12 months N (%)	Baseline N (%)	12 months N (%)		
Shortness of breath						
Wheezing						
Cough						
Phlegm						

Table 7– Percentage participants reporting an adverse reaction at least once

% (N) reporting Adverse Reaction	EC	NRT	P-value
Nausea			
Sleep disturbances			
Throat/mouth irritation			

Table 8 – Differences in urges to smoke at 1 and 4 weeks post quit (abstainers only)

Symptom	1 week post quit		P-value	Mean difference (95% CI)	4 weeks post quit		P-value	Mean difference (95% CI)
	EC	NRT			EC	NRT		
Frequency of urge to smoke – mean (SD)								
Strength of urge to smoke – mean (SD)								
Composite urge score – mean (SD)								

Table 9 – Differences in urges to smoke at 1 and 4 weeks post quit (whole sample)

Symptom	1 week post quit		P-value	Mean difference (95% CI)	4 weeks post quit		P-value	Mean difference (95% CI)
	EC	NRT			EC	NRT		
Frequency of urge to smoke – mean (SD)								
Strength of urge to smoke – mean (SD)								
Composite urge score – mean (SD)								

Table 10 – Change in withdrawal symptoms between baseline and 4-weeks post TQD (abstainers only)

Symptom	NRT (n=)	EC (n=)	P-value	Mean difference, (95% CI)
Depressed – mean (SD)				
Irritable – mean (SD)				
Restless – mean (SD)				
Hungry – mean (SD)				
Poor concentration – mean (SD)				
Composite MPSS score – mean (SD)				

Table 11 – Change in withdrawal symptoms between baseline and 4-weeks post TQD (whole sample)

Symptom	NRT (n=)	EC (n=)	P-value	Mean difference (95% CI)
Depressed – mean (SD)				
Irritable – mean (SD)				
Restless – mean (SD)				
Hungry – mean (SD)				
Poor concentration – mean (SD)				
Composite MPSS score – mean (SD)				

Health economics tables

Table 12: Breakdown of intervention cost (mean [S.D.])

Cost item	NRT (n=xxx)	EC (n=xxx)
Behavioural support sessions		
NRT/EC supplies		
Information sheets		
Total		

Table 13: Unit cost

Services	Unit cost	Sources
Smoking cessation help		
GP		
NHS SSS		
NHS Smoking Helpline service		
Pharmacotherapies		
Patch		
Gum		
Microtab		
Inhaler		
Lozenge		
Spray		
Mouthstrip		
Varenicline		
Bupropion		
Health resources use		
A & E		
Outpatient		
Inpatient		
Day case		
Emergency ambulance		

GP (in office)		
Practice nurse (in office)		
GP (home visit)		
Practice nurse (home visit)		
Prescription		

Table 14: Usage and mean cost of services (mean [S.D.]

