2. A little of the time
3. Some of the time
4. A lot of the time
5. Almost all of the time
6. All of the time

Q7. How strong have these urges been?

1. No urges
2. Slight
3. Moderate
4. Strong
5. Very strong
6. Extremely strong

Definition: Changes in withdrawal symptoms between baseline and 4 weeks on following scale: not at all, slightly, somewhat, very, extremely.

Data source: Q+1 and Q+4 Post Quit CRF,

Q5. For each of the following (depressed, hungry, irritable, poor concentration, restless) rate how you have been feeling over the past week:

1. Not at all
2. Slightly
3. Somewhat
4. Very
5. Extremely

9. Treatment ratings

Definition: Ratings of helpfulness on the following scale: not at all, slightly, somewhat, very, extremely

Data source: Q+1 and Q+4 post quit CRFs

Q8c. Since your last visit/contact how helpful did you find your allocated product(s) in keeping you away from normal cigarettes?

1. Not at all
2. Slightly
3. Somewhat
4. Very
5. Extremely

Definition: Ratings of taste on the following scale: much worse than normal cigarettes, a little worse than normal cigarettes, the same as normal cigarettes, a little better than normal cigarettes, much better than normal cigarettes

Data source: Q+1 and Q+4 post quit CRFs

Q10. How good did it taste?

1. much worse than normal cigarettes
2. a little worse than normal cigarettes
3. the same as normal cigarettes
4. a little better than normal cigarettes
5. much better than normal cigarettes

Definition: Ratings of satisfaction on the following scale: much worse than normal cigarettes, a little worse than normal cigarettes, the same as normal cigarettes, a little better than normal cigarettes, much better than normal cigarettes

Data source: Q+1 and Q+4 post quit CRFs

Q11. How satisfying was it?

1. Much less than normal cigarettes
2. A little less than normal cigarettes
3. The same as normal cigarettes
4. A little more than normal cigarettes
5. Much more than normal cigarettes

10. Adverse reactions (AR) **Definition:** % (N) reporting 'Yes' to adverse reaction on at least one post quit session.

Data source: Health Problems CRF checklist at all post quit sessions (specifically nausea, sleep disturbance and throat/mouth irritation questions).

11. Change in respiratory problems **Definition:** Participants are defined as experiencing the health problem if they responding 'Yes' to it and the given time point.

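### Adverse reactions are compared as reported at least once, with no stated denominator and no allowance for checklists completed, so unequal contact between arms could appear as a difference in tolerability

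*SAP*

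**What the plan says.** The SAP's section on adverse reactions says that the frequency of participants reporting each AR "at least once will be compared between arms using Chi squared test". Appendix 3, item 10, defines a case as a participant "reporting 'Yes' to adverse reaction on at least one post quit session" and gives the source as the "Health Problems CRF checklist at all post quit sessions".

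The section on timing of data collection schedules "Treatment sessions, 1, 2, 3 and 4 weeks post TQD", then follow-up at 24 and 52 weeks. A participant can therefore contribute up to six checklists.

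On who is counted, the general analysis principles say that "all participants with a recorded outcome will be included in the analysis". They do not say whether someone with one checklist out of six has a recorded AR outcome. No missing-data rule covers ARs: the outcome rules deal with abstinence and the health-economic rules with service use and EQ-5D.

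The same general principles promise, for every outcome, the number analysed by arm and a treatment effect with a 95% confidence interval. The shell of Table 7, "Percentage participants reporting an adverse reaction at least once", has columns for EC, NRT and a p-value only.

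**The concern.** The chance of at least one positive report rises with the number of times a person is asked. Participants know their product from the quit date, so attendance may come to differ by arm. The two percentages in Table 7 would then mix tolerability with opportunity to report. An arm that keeps people in contact could look worse, and an arm that loses them could look better.

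AR rates on EC compared with NRT are secondary objective 6, and this is the only formal comparison of the three named ARs. The SAP shows awareness of the general risk. Randomisation is placed at the quit date to limit differential drop-out, and Table 2 compares contacts completed by arm. That count, however, leaves out weeks 2 and 3, includes the pre-quit session and does not enter the AR analysis.

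**Working it through.** The SAP states no AR rate, AR power or attendance figure, so there is none to reproduce.

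**Inputs from the SAP:** 443 per arm, 1:1 allocation, two-sided 5% level, up to six checklists.

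**Assumptions:** the chance q of a positive report per checklist (the same in both arms), the number k of checklists completed, and the within-person correlation rho of reports. Attendance is taken to be unrelated to ARs.

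**1. Independent reports.** P(ever) = 1 − (1 − q)^k. With q = 0.10:
- k = 4: 1 − 0.9^4 = 34.4%
- k = 5: 1 − 0.9^5 = 41.0%
- Risk ratio = 0.4095/0.3439 = 1.19, with no true difference.

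Chance of p < 0.05 by the two-proportion normal approximation:
- Pooled proportion = 0.3767; standard error under no difference = √(2 × 0.3767 × 0.6233/443) = 0.0326.
- Unpooled standard error = 0.0325.
- Φ((0.0656 − 1.96 × 0.0326)/0.0325) ≈ 0.52.

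The same 4 v 5 comparison gives 32% at q = 0.05 and 72% at q = 0.20. A gap of 4.5 v 5 at q = 0.10 gives 16%.

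**2. Correlated reports.** In a beta-binomial model with a + b = 1/rho − 1 and a = q(a + b), P(ever) = 1 − ∏(b + j)/(a + b + j), for j = 0 to k − 1. For q = 0.10 and 4 v 5 checklists:

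| rho | 4 checklists | 5 checklists | False rejection |
|---|---|---|---|
| 0 | 34.4% | 41.0% | 52% |
| 0.3 | 24.3% | 27.1% | 16% |
| 0.5 | 19.4% | 21.0% | 9% |
| 0.6 | 17.3% | 18.5% | 7% |

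**3. Size of the completion gap.** With session attendance A, P(ever) = 1 − (1 − qA)^6 for independent reports. At q = 0.10:
- 80% v 70% attendance (mean 4.8 v 4.2 checklists): 39.4% v 35.3%, false rejection about 24%.
- 80% v 78%: 39.4% v 38.6%, about 6%, which is close to nominal.

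**4. Denominator.** This was simulated with 500 runs per setting and monotone drop-out. Retention was 0.95 v 0.90 per session (about 5.0 v 4.2 checklists), with q = 0.10. False rejection was:

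| rho | All randomised | At least one checklist |
|---|---|---|
| 0 | 44% | 25% |
| 0.3 | 21% | 10% |
| 0.6 | 13% | 7% |

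With equal retention (0.95 in both arms), rejection was 3–7% across the settings run (q = 0.05 to 0.20), which is nominal within simulation error.

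**5. Does a per-checklist rate remove the artefact?** With retention 0.95 v 0.85 (mean 5.04 v 3.53 checklists), q = 0.10 and rho = 0.3, the at-least-once percentages were 25.7% v 19.6% (all randomised) or 27.0% v 23.0% (at least one checklist). The per-checklist rates in the same data were 10.0% v 9.9%.

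**The case against.** Reporting at least once, per participant, is a standard harms summary. The 52% figure needs independent reports and a full one-checklist gap, and symptoms such as sleep disturbance may well recur in the same people. Support and follow-up contacts are meant to be identical in both arms, everyone is to be followed up even after discontinuing, and Table 2 would reveal much of any imbalance. The recorded-outcome rule can be read as excluding people with no checklist, which shrinks the artefact. The checklist's recall period is in a CRF that is not shown. If it asks about the time since the last contact, a later form would cover a missed visit and only final drop-out would matter. All of this stands, and it limits the size of the problem. It does not supply a denominator or an allowance for unequal completion.

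A reader might go further in three ways that the SAP does not support:
- That this is its only formal harm comparison. Respiratory symptoms are also tested, at fixed times (baseline and 12 months).
- That missed checklists are necessarily scored as No. That is one reading of an unstated rule.
- That the EC arm will be the one affected, or that attendance will differ at all. No attendance by arm is given.

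**Conclusion.** The point holds as a conditional weakness. The AR definition depends on the number of checklists completed, and the SAP neither fixes the denominator nor allows for that number. If completion differs, the better-retained arm will tend to show more ARs at equal tolerability.

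For a one-checklist gap at 10% per checklist, false rejection runs from about 7% to 52% as rho falls from 0.6 to 0. It is near 5% when completion is almost equal, and smaller when people with no checklist are left out. These figures assume equal tolerability and attendance unrelated to ARs. If people leave because of a reaction not yet reported, the poorly retained arm would look better still. Neither the actual size nor the arm affected can be determined from the SAP. An improvement is worthwhile because it is cheap, but the planned comparison does not have to be withdrawn.

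**What to change.** - Keep the at-least-once comparison and state its denominator, including how participants with no checklist or only some are counted.
- In Table 7, add the number analysed, the number of AR checklists completed per arm, and an effect estimate with 95% confidence interval.
- Add a supporting comparison of each AR at weeks 1 and 4, with those completing that checklist as denominator. These are the time points already used for product ratings and urges to smoke. The alternative is a repeated-measures logistic model with one row per completed checklist and terms for arm and visit. Either should report an effect estimate and confidence interval.
- Say that any at-least-once difference will be interpreted in the light of that analysis.

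The cost is some SAP wording, a few extra tests and a longer table, all on data already collected. There are two limits. These analyses remove the checklist-count artefact but not bias from participants who leave because of an unreported reaction. The per-checklist model also estimates average prevalence rather than whether a reaction ever occurred, so it complements the planned comparison and does not replace it.

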Q2 (CO reading) on Q+4 post Quit CRF (only for those who attended Q+4 in person and self-reported abstinence). NB. As per definition in primary outcome section, those who do not provide a CO reading at 4 weeks post TQD but self-report abstinence at this time point will be assumed to be abstinent at 52 weeks follow up providing they report no more than 5 cigarettes smoked since 2 weeks post TQD at 52 weeks accompanied by a CO reading of < 8ppm at week 52. Those who self-report abstinence at 4 weeks post TQD but fail CO validation at 4 weeks post TQD (> 8ppm) will **not** be counted as abstinent at 52 week follow up.

At Q+52:

Q3. Since two weeks after your quit date, have you smoked regular cigarettes at all? (circle ONE)

1. Not a single puff
2. Just a few puffs
3. ≤ 5 cigs in total
4. > 5 cigs in total

NB. as per definition in primary outcome section, where a participant reports smoking 1-5 cigarettes at more than one session/follow up but reports smoking no more than 5 cigarettes in total since 2 weeks post TQD at 52 week follow up, they will be assumed to have smoked no more than 5 cigarettes in total since 2 weeks post TQD and will meet the primary outcome definition providing their self-report is validated by a CO reading of <8ppm at the 52 week follow up.

Where a participant reports being 'currently quit' at 52 week follow up, but has not been contactable to provide any other information, they will be not counted as a 52 weeks sustained abstainer since they will not have been contactable to arrange a CO validation.

Where a participant reports being 'currently quit' at 4 and/or 24 weeks post TQD and has not been contactable to provide further information at these time points, but then reports smoking no more than 5 cigarettes in total since 2 weeks post TQD at 52 week follow up, they will be assumed to have smoked no more than 5 cigarettes in total since 2 weeks post TQD and will meet the primary outcome definition providing their self-report is validated by a CO reading of <8ppm at the 52 week follow up.

Q+52 Validation Visit CRF

2. Record carbon monoxide in expired breath (ppm)

Secondary Outcomes

1. CO validated sustained abstinence between 24 and 52 weeks post TQD

Definition: No more than 5 cigarettes smoked between weeks 24 and 52 accompanied by a CO reading of < 8ppm at week 52.

Data source: Q+52 CRF

Have you smoked regular cigarettes at all in the last 6 months? (circle ONE)

1. Not a single puff
2. Just a few puffs
3. ≤ 5 cigs in total
4. > 5 cigs in total
5. Currently quit – no other info

NB. Where a participant reports being 'currently quit' at 52 week follow up, but has not been contactable to provide any other information, they will be not counted as a 24-52 week sustained abstainer since they will not have been contactable to arrange a CO validation.

Q+52 Validation Visit CRF

3. Record carbon monoxide in expired breath (ppm)

2. CO validated sustained abstinence at 4 weeks post TQD

Definition: Not a single puff of a cigarette in the last 2 weeks at 4 week follow up accompanied by a CO reading of < 8ppm at 4 week follow up.

Data source: Q+3 and Q+4 CRF

Q3. Have you smoked regular cigarettes at all since your last visit/contact? (circle ONE)

1. Not a single puff
2. Just a few puffs
3. ≤ 5 cigs in total
4. > 5 cigs in total
5. Currently quit – no other info (shown at Q+4, 24 and 52 only)

NB. As per the definition in the secondary outcomes section, where a participant misses Q+3 but reports not a single puff since their last visit at 4 weeks post TQD, accompanied by a CO reading of < 8ppm at 4 weeks, they will be counted as a CO validated abstainer at 4 weeks post TQD.

Where a participant reports being ‘currently quit’ at 4 weeks post TQD, but has not been contactable to provide any other information, they will not be counted as a 4 week abstainer since they will not have been contactable to arrange a CO validation.

Q2. Record carbon monoxide in expired breath (ppm) on Q+4 post quit CRF only

3. Sustained abstinence at 24 weeks post TQD

Definition: No more than 5 cigarettes smoked since 2 weeks post TQD at 24 weeks

Data source: Q+3, Q+4 and Q+24 CRF

Have you smoked regular cigarettes at all since your last visit/contact? (circle ONE)

1. Not a single puff
2. Just a few puffs
3. ≤ 5 cigs in total
4. > 5 cigs in total
5. Currently quit – no other info (shown at Q+4, 24 and 52 only)

NB. As per definition in secondary outcome section, where data is missing for 3 and/or 4 weeks post TQD participants will be assumed to be abstinent at 24 weeks post TQD providing they report no more than 5 cigarettes smoked since their last visit at 24 weeks.

Where a participant reports smoking 1-5 cigarettes at 3 and 4 weeks post TQD but reports smoking no more than 5 cigarettes in total since their last visit at 24 weeks, they will be assumed to have smoked less than 5 cigarettes in total since 2 weeks post TQD at 24 weeks.

Where a participant reports being 'currently quit' at 24 weeks post TQD, but has not been contactable to provide any other information, they will be counted as having smoked no more than 5 cigarettes since their last visit, and included as a 24 week sustained abstainer.

4. 7-day point prevalence
at 4-weeks post TQD

Definition: Not a single puff in the last 7-days

Data source: Q+4 CRF

If you have smoked since your last visit/contact, did you smoke at all in the last 7 days?

1. Yes
2. No

5. 7-day point prevalence
at 24-weeks post TQD

Definition: Not a single puff in the last 7-days

Data source: Q+24 CRF

If you have smoked since your last visit/contact, did you smoke at all in the last 7 days?

1. Yes
2. No

6. 7-day point prevalence
at 52-weeks post TQD

Definition: Not a single puff in the last 7-days

Data source: Q+52 CRF

Have you smoked at all in the last 7 days?

1. Yes
2. No

7. Smoking reduction in participants who did not achieve abstinence at 52 weeks

Definition: Daily cigarette consumption of at least 50% of baseline consumption accompanied by a CO reading of 50% of baseline

Data source: Q+52 Post Quit CRF

3b. How many cigarettes per day are you smoking now?

3c. Percentage reduction in number of cigarettes smoked from start of study

Q+52 Validation Visit CRF

3. Record carbon monoxide in expired breath (ppm)

NB. Where participants have CO<10 at baseline and report 50% or more cigarette per day reduction at 52 weeks post TQD, sensitivity analyses will be carried out including and excluding them.

A sub-analysis of self-reported daily cigarette consumption at 52 week follow up reduced by at least 50% of baseline consumption without accompanied CO readings will also be conducted.

Data source: Q+52 Post Quit CRF

3b. How many cigarettes per day are you smoking now?

3c. Percentage reduction in number of cigarettes smoked from start of study

8. Changes in urges to smoke and other tobacco withdrawal symptoms at 1 and 4 weeks.

Definition: Differences in the ratings of urge frequency at 1 and 4 weeks post quit on following scale: not at all, a little of the time, some of the time, a lot of time, almost all of the time, all of the time.

Differences in the ratings of urge strength at 1 and 4 weeks post quit on following scale: no urges, slight, moderate, strong, very strong, extremely strong.

Data source: Q+1 and Q+4 Post Quit CRF

Q6. How much of the time have you felt the urge to smoke over the past week?

1. Not at all
2. A little of the time
3. Some of the time
4. A lot of the time
5. Almost all of the time
6. All of the time

Q7. How strong have these urges been?

1. No urges
2. Slight
3. Moderate
4. Strong
5. Very strong
6. Extremely strong

Definition: Changes in withdrawal symptoms between baseline and 4 weeks on following scale: not at all, slightly, somewhat, very, extremely.

Data source: Q+1 and Q+4 Post Quit CRF,

Q5. For each of the following (depressed, hungry, irritable, poor concentration, restless) rate how you have been feeling over the past week:

1. Not at all
2. Slightly
3. Somewhat
4. Very
5. Extremely

9. Treatment ratings

Definition: Ratings of helpfulness on the following scale: not at all, slightly, somewhat, very, extremely

Data source: Q+1 and Q+4 post quit CRFs

Q8c. Since your last visit/contact how helpful did you find your allocated product(s) in keeping you away from normal cigarettes?

1. Not at all
2. Slightly
3. Somewhat
4. Very
5. Extremely

Definition: Ratings of taste on the following scale: much worse than normal cigarettes, a little worse than normal cigarettes, the same as normal cigarettes, a little better than normal cigarettes, much better than normal cigarettes

Data source: Q+1 and Q+4 post quit CRFs

Q10. How good did it taste?

1. much worse than normal cigarettes
2. a little worse than normal cigarettes
3. the same as normal cigarettes
4. a little better than normal cigarettes
5. much better than normal cigarettes

Definition: Ratings of satisfaction on the following scale: much worse than normal cigarettes, a little worse than normal cigarettes, the same as normal cigarettes, a little better than normal cigarettes, much better than normal cigarettes

Data source: Q+1 and Q+4 post quit CRFs

Q11. How satisfying was it?

1. Much less than normal cigarettes
2. A little less than normal cigarettes
3. The same as normal cigarettes
4. A little more than normal cigarettes
5. Much more than normal cigarettes

10. Adverse reactions (AR) **Definition:** % (N) reporting 'Yes' to adverse reaction on at least one post quit session.

Data source: Health Problems CRF checklist at all post quit sessions (specifically nausea, sleep disturbance and throat/mouth irritation questions).

11. Change in respiratory problems **Definition:** Participants are defined as experiencing the health problem if they responding 'Yes' to it and the given time point.

Data source: Health Problems CRF checklist (specifically shortness of breath, wheezing, cough and phlegm questions) at baseline and Q+52.
